### **Tertiary Outcome Measures:**

- Quality of Life- Odor reduction [ Time Frame: Baseline (0 weeks), 4 weeks, 8 weeks, 12 weeks ]

- Quality of Life- Itch reduction [ Time Frame: Baseline (0 weeks), 4 weeks, 8 weeks, 12 weeks ]
- Quality of Life- Visual appearance
- Number of reapplications / Size of units applied
- Incidence of adverse events (e.g. infection, etc.)
- Cost effectiveness / Economic model (Amount of product usage, length of treatment)
- Intraoperative notes / Ease of Use, Handling (Feedback on handling / ease of use and placement)
- Billing / Coding / Reimbursement information

## 4. PATIENT SELECTION

### 4.1. Inclusion Criteria

- Male or female age 18 or older
- Patient's ulcer must be diabetic in origin, located at least in part on the plantar surface and larger than 1cm^2 after the run-in period. Debridement will be done prior to randomization. Subject's informed consent for participating in this study, must be obtained prior to proceeding with sharp debridement
- Patients with Type 1 or Type 2 diabetes (criteria for the diagnosis of diabetes mellitus per ADA).
- Ulcer must be present for a minimum of four weeks before enrollment/randomization, with documented failure of prior treatment to heal the wound. A two-week run in period will precede enrollment/randomization in the trial to document the indolent nature of the patients selected
- Patient does not exhibit clinical signs / symptoms of infection upon gross observation (at least 3 of the following: pain, redness, purulence, exudate, temperature) or have been diagnosed with an active infection at time of screening
- Patient is willing to provide informed consent and is willing to participate in all procedures and follow up evaluations necessary to complete the study
- Patient has adequate control of diabetes, as demonstrated by one of the following within 30 days of screening:
  - HbA1c < 12%

- Serum Creatinine < 3.0mg/dl
- Patient has adequate circulation to the affected extremity, as demonstrated by one of the following within the past 60 days of the first screening visit:
  - Dorsum transcutaneous oxygen test (TcPO2) with results  $\geq 30$ mmHg, OR
  - ABIs with results of  $\geq 0.7$  and  $\leq 1.5$ , OR
  - Doppler arterial waveforms, which are triphasic or biphasic at the ankle of affected leg

#### **4.2. Exclusion Criteria**

- Patients presenting with an ulcer probing to bone (UT Grade IIIA-D)
- Patients whose index diabetic foot ulcers are greater than  $25\text{cm}^2$
- Patient has an additional wound within 3cm of the study wound
- Patients not in reasonable metabolic control
- Patients with a known history of poor compliance with medical treatments
- Patients who have been previously enrolled into this study, or are presently participating in a clinical trial with DFU indications
- Patients with known or suspected local skin malignancy to the index diabetic ulcer
- Patients diagnosed with autoimmune connective tissues diseases
- Patients that have received a graft material on the study ulcer within the previous 30 days
- Patients who are pregnant or breast feeding
- Patients who are taking medications that are considered immune system modulator
- Study wound has closed  $> 30\%$  over the two-week run-in period
- Patients with a known allergy to resorbable suture materials

#### **5. STUDY CONDUCT**

The schedule of events for this study is outlined in Appendix A.

## 5.1. Enrollment Procedures

Prior to enrollment, patients expressing an interest in participation will proceed with the inclusion/exclusion eligibility interview and informed consent process. An enrolled patient will be one who completes the eligibility interview, signs the Informed Consent form and receives the Restrata™ device.

## 5.2. Device Application / Follow-up Care Procedures

Please refer to Appendix B for a list of supplies that will be provided by Acera for wound assessments / follow-up care procedures.

### 1) WOUND BED PREPARATION:

- Review patient's medical history and physical examination.
- Complete the Informed Consent process.
- Perform gross observation of the wound site for evidence of infection.
- Conduct all pre-application Quality of Life assessments and surveys.
- Prepare the wound bed using standard methods to ensure it is free of exudate and devitalized tissue. An initial excision or debridement of the wound may be necessary to ensure the wound edges contain viable tissue.
- Wait for any bleeding to stop before applying Restrata™ Wound Matrix.
- Cleanse the wound thoroughly with sterile saline prior to application of Restrata™ Wound Matrix.

### 2) PREPARATION OF RESTRATA™ WOUND MATRIX

- Measure the wound area and select the appropriate size sheet of Restrata™.
- **Heavily fenestrate Restrata™ with a scalpel prior to application.** Restrata™ must be fenestrated prior to use in any wound prone to exudate in order to permit effective exudate management.
- Restrata™ is packaged in a nested pouch configuration. Peel open the outer foil pouch starting from the chevron sealed edge. The inner TyVek® pouch is sterile and may be placed on the sterile field.
- Rinse surgical gloves, if necessary, to remove any glove powder prior to touching the product.
- Restrata™ can be cut to the desired shape in a wet or dry state. In order to increase pliability of the product, hydrate Restrata™ in warm, sterile, hypertonic solution (i.e. saline, water, etc.) for a minimum of 1 minute.

**3) APPLICATION OF RESTRATA™ WOUND MATRIX:**

- Apply Restrata™ with either side towards the wound bed, and position to completely contact the entire surface of the wound bed and extend slightly beyond wound margins. Restrata™ can be repositioned as necessary.
- Securely anchor Restrata™ Wound Matrix as needed with suture or Steristrips.
- Apply a non-adherent primary wound dressing over the Restrata™ Wound Matrix. No topical treatments of any kind should come into contact with Restrata™ after it is placed.
- To prevent dislodgement of device, apply appropriate secondary dressing or compression to maintain dressing adherence (e.g., multi-layer compression bandage system, or other appropriate dressing), manage the wound exudate, keep the Restrata™ Wound Matrix moist, and keep all layers securely in place. The optimum secondary dressing is determined by wound location, size, depth and user preference.
- To ensure off-loading, each patient will be fitted with an identical CAM boot provided by Acera to encourage standardization of wound treatment. The investigator may prescribe a CAM boot other than the one provided by the sponsor, without being considered a protocol deviation, but only if the investigator determines the provided CAM boot is insufficient for complete off-loading of the wound area.
- Discard any unused pieces of Restrata™ Wound Matrix.

**4) DRESSING CHANGES:**

- Change the secondary dressing as appropriate. Frequency of secondary dressing change will be dependent upon volume of exudate produced, type of dressing used and the clinician's need to inspect the wound bed for signs of infection or healing.
- Unless infected, the following dressing types should not be applied as part of dressing changes: hydrocolloids, foams, alginates, or silver-impregnated dressings.

**5) WOUND ASSESSMENT:**

- Carefully assess the wound and record healing progression such as wound dimensions, wound depth, signs of infection, description of exudate present, and wound bed characteristics.
- Evaluate the amount of Restrata™ Wound Matrix remaining in the wound and describe the appearance of the material.

- If Restrata™ Wound Matrix is completely intact (no resorption has occurred) and the wound is clean and clear of infection, then leave the matrix in place and cover with primary and secondary dressings.
- If any of the Restrata™ Wound Matrix material has resorbed than remove the remaining material and replace with a new piece of Restrata™ Wound Matrix (refer to section 6).
- Administer the VAS Foot and Ankle questionnaire.

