## **6) REAPPLICATION OF RESTRATA™ WOUND MATRIX:**

- Restrata™ Wound Matrix needs to be reapplied weekly over previously absorbed material (see section 3) steps 2 & 3).
  - However, if Restrata™ Wound Matrix is completely intact, no material, resorption has occurred and the wound is clean and clear of infection than the matrix does not have to be reapplied.
- In the event the material does need to be removed from the wound bed prior to reapplication, use warm (37°C) sterile saline to continuously rinse the wound site to help detach the material, so as not to cause further damage to the wound bed. Forced removal may result in wound reinjury.

*NOTE: If excess exudate collects under Restrata™, the material should be thoroughly fenestrated to allow the exudate to drain.*

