### **5.4. Follow-Up Procedures (Weekly up to 12 weeks or until complete closure is first identified with a confirmation visit within 2 weeks thereafter; window for all visits is $\pm$ 3 days)**

At each of the interim timepoints subjects will return to the clinic for analysis / assessment of the following as indicated in the Schedule of Events in Appendix A:

- Measurement of wound area via acetate tracing
- Documentation of wound appearance via photograph
- Documentation of wound closure (if present)
- Gross observation of wound for evidence of infection

- Assessment of Quality of Life- Odor (only at 4, 8, 12 weeks  $\pm$  3 days)
- Assessment of Quality of Life- Itch (only at 4, 8, 12 weeks  $\pm$  3 days)
- Assessment of Quality of Life- Visual appearance
- Codes used to submit for reimbursement and amount (if any) reimbursed

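### Do steps 5 and 6 of Section 5.2 conflict on residual matrix in a way that calls for a change to the plan?

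*Combined protocol and SAP*

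**What the plan says.** Section 5.2 (Device Application / Follow-up Care Procedures) deals with residual matrix in two consecutive steps. Both are current text: the revision summary lists subsections 4, 5 and 6 of Section 5.2 among the parts updated when reapplication moved from four-weekly to weekly.

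Step 5 (Wound Assessment) has two branches. If the matrix "is completely intact (no resorption has occurred) and the wound is clean and clear of infection, then leave the matrix in place". If any of the "material has resorbed than remove the remaining material and replace with a new piece", with a closing parenthesis that sends the reader to section 6. Step 5 also asks staff to judge how much matrix remains and to describe how it looks.

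Step 6 (Reapplication) starts from a default: the matrix "needs to be reapplied weekly over previously absorbed material". It makes one exception: if the matrix is intact and "the wound is clean and clear of infection than the matrix does not have to be reapplied". It then describes a warm saline rinse, introduced by "In the event the material does need to be removed from the wound bed prior to reapplication", and adds a caution: "Forced removal may result in wound reinjury".

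Three other places bear on the point. Section 6.2 leaves the choice between reapplication and an ordinary dressing change to gross observation, without criteria. Step 4 foresees infection during treatment, with a rule that opens "Unless infected, the following dressing types should not be applied as part of dressing changes". Section 5.4 lists "Gross observation of wound for evidence of infection" among the follow-up assessments.

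**The concern.** Two things look wrong on a first reading.

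- **Partly resorbed matrix.** Step 5 orders removal of the remainder without condition. Step 6 speaks of reapplying over absorbed material and treats removal as a contingency whose trigger it does not state. One site might strip the remnant while another covers it.
- **Intact matrix on an infected or unclean wound.** Neither branch of step 5 fits this state. Step 6 waives reapplication only when the wound is clean and uninfected, so its weekly default appears to apply. It does not say whether the intact piece comes off first.

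If sites (up to 8 are planned) acted differently, the variation would fall on the wound that supplies the closure and area outcomes. It could also alter the number of reapplications, which is a tertiary outcome and feeds product usage in the economic outcome.

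**Working it through.** The plan gives no figure to reproduce, so the check sets the two steps side by side. Step 5 distinguishes a completely intact matrix from any resorption, and both steps distinguish a clean, uninfected wound from one that is not. That gives 2 × 2 = 4 states.

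| Matrix | Wound | Step 5 | Step 6 | Comparison |
|---|---|---|---|---|
| Intact | Clean, uninfected | Leave and cover | Need not reapply | Compatible; leaving it meets both |
| Any resorption | Clean, uninfected | Remove remainder, place new piece | New piece; removal if needed | Same on the new piece, loose on removal |
| Any resorption | Infected or unclean | As above | As above | As above |
| Intact | Infected or unclean | No branch | Exception not met; default by implication | Gap in step 5 |

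A tally of these rows does not measure size. Splitting off a fully resorbed state, which step 5 does not do, would add two rows on which the steps agree, because nothing would be left to remove.

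**Rows 2 and 3.** Can a site obey both steps at once?

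1. The step 5 instruction ends with a pointer to section 6. Step 6 uses the word section in the same way for the numbered steps of 5.2, so the pointer is naturally read as step 6.
2. On that reading step 5 supplies the condition that step 6 leaves open, and step 6 supplies the rinsing method.
3. Step 6 refers to material that has been absorbed, not material that remains. Absorbed material can mean material already gone. Placing a new piece after the remainder is removed then satisfies step 6 as well.
4. Both steps end with one new piece placed. The difference in the reapplication count is 1 − 1 = 0.

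So at least one course of action meets both texts. Whether it is the clinically preferable one is not judged here.

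**Row 4.** Step 5 is silent and step 6 speaks only by negation of its exception. Its default also describes reapplication over absorbed material, which does not fit an intact piece. This is a missing instruction with an implied rule beside it, not two opposed instructions. The count could differ by 0 or 1 at such a visit.

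**Ceiling.** The device application row in Appendix A has 12 marks, read as Weeks 0 to 11 (the table extraction is imperfect). Taking away the first application, 12 − 1 = 11 reapplication visits per patient at most, and fewer with earlier closure. The documents give no frequency for row 4, so no expected difference can be computed.

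**Link to the analysis.** Section 8.1 plans descriptive statistics, with confidence intervals where appropriate. The primary outcome is the percentage of wounds closed. Neither the handling of residual matrix nor the number of pieces enters that percentage, and the reapplication outcome is a count of what was done.

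**The case for a change.** The strongest reply is that reading the steps in sequence does not rescue everything. Step 6 is more than technique, since it opens with its own default and its own exception. The sequential reading also does nothing for an intact matrix on an infected wound, a state the protocol plainly foresees: there is an infection rule for dressings, infection is checked at follow-up, and the tertiary outcomes name it as an example of an adverse event. Section 6.2 hands over the decision without criteria. The caution about reinjury shows that removal is not a trivial matter. The stated aim is to inform a randomised trial, so an unclear procedure could be carried forward, and rewording would be cheap.

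Part of this stands. The conditional wording of step 6 does not match the unconditional wording of step 5, and the gap is real.

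The consequences are thinner than they appear. The reinjury caution concerns forced removal, and the same bullet gives the rinse meant to avoid it. Section 6.2 already gives judgement at the visit a stated role. Step 5 has staff assess the amount and appearance of remaining matrix, and a device application form is scheduled across the treatment visits. Whether that form records what was done with the remnant cannot be checked, because its pages are not in the documents. An amendment would need sponsor and IRB/IEC approval under Section 10.1, and no stated result or conclusion has been shown to change with it.

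**Conclusion.** The observation is correct as a matter of wording, but it does not call for a change to the plan. For partly resorbed matrix the steps can be followed together and give the same count. For an intact matrix on an infected or unclean wound there is a missing detail that sites settle through the observation Section 6.2 assigns to them. The possible difference there is at most 1 reapplication per such visit, within a ceiling of 11 visits per patient. It bears on a descriptive tertiary count and on product usage. No effect on closure or area can be derived in either direction.

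This rests on three assumptions: that the pointer in step 5 means step 6 of Section 5.2, that the 12 marks in Appendix A are Weeks 0 to 11, and that the application form shows whether a new piece was placed. How each state should be handled clinically, and any tidying of the two steps, belongs to the sponsor's clinical and device leads; no view is taken on which instruction is right.

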## **6) REAPPLICATION OF RESTRATA™ WOUND MATRIX:**

- Restrata™ Wound Matrix needs to be reapplied weekly over previously absorbed material (see section 3) steps 2 & 3).
  - However, if Restrata™ Wound Matrix is completely intact, no material, resorption has occurred and the wound is clean and clear of infection than the matrix does not have to be reapplied.
- In the event the material does need to be removed from the wound bed prior to reapplication, use warm (37°C) sterile saline to continuously rinse the wound site to help detach the material, so as not to cause further damage to the wound bed. Forced removal may result in wound reinjury.

*NOTE: If excess exudate collects under Restrata™, the material should be thoroughly fenestrated to allow the exudate to drain.*

### **5.3. Post-Application Procedures**

- Patients should be instructed on how to care for the surgical site, utilize the CAM walker, and keep the surgical site moist, and clean.
- Patients are required to return to the clinic every week for post-operative analysis of the wound site.

### **5.4. Follow-Up Procedures (Weekly up to 12 weeks or until complete closure is first identified with a confirmation visit within 2 weeks thereafter; window for all visits is $\pm$ 3 days)**

At each of the interim timepoints subjects will return to the clinic for analysis / assessment of the following as indicated in the Schedule of Events in Appendix A:

- Measurement of wound area via acetate tracing
- Documentation of wound appearance via photograph
- Documentation of wound closure (if present)
- Gross observation of wound for evidence of infection

- Assessment of Quality of Life- Odor (only at 4, 8, 12 weeks  $\pm$  3 days)
- Assessment of Quality of Life- Itch (only at 4, 8, 12 weeks  $\pm$  3 days)
- Assessment of Quality of Life- Visual appearance
- Codes used to submit for reimbursement and amount (if any) reimbursed

## **5.5. Adverse Event Assessments**

Assessment of safety is documented on the Adverse Events forms. The investigator should document any reported adverse events that occur outside of interval visits. Documentation of Adverse Events should include type, severity and relatedness to the device.

## **5.6. Early Withdrawal**

Patients who withdraw prior to the 12 week endpoint who have not yet been confirmed to have completely closed at the confirmation visit will be contacted by phone and/or mail. The purpose of making contact will be to determine the status of the wound to the best of the patient's ability (i.e., healed, not healed, seeking additional treatment, not seeking additional treatment) and to complete as many of the patient-reported outcomes questionnaires as possible. Information obtained on these withdrawn patients will be counted toward the actual follow-up rate, but used only for the analysis of tertiary endpoints.

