## **7. ADVERSE EVENT (AE)**

### **7.1. Principal Investigator Responsibilities**

The Principal Investigator (PI) and/or staff participating in the study shall document all adverse events as defined in section 7.3 of this protocol. The severity of the AE and its relationship to the procedure / device will also be assessed by the PI. The PI will document on the CRF any relatedness descriptions that might apply to the AE (e.g. none, possible, probable, and definite). The sponsor will designate a monitor to review patient medical records at the study locations for indications of adverse events throughout the study to ensure appropriate documentation and reporting.

Reimbursement data collected in the study requires purchase of the Restrata™ material so that the investigator is able to submit for reimbursement from payers. The purchase price will be agreed upon within the Clinical Trial Agreement.

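### The contact with withdrawn patients does not ask about adverse events or the reason for leaving, so events after the last visit may be under-ascertained while the patient still counts toward follow-up

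*Combined protocol and SAP*

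**What the plan says.** Section 5.6 (Early Withdrawal) gives the phone or mail contact two purposes. One is to learn the state of the wound, with the possible answers listed as "healed, not healed, seeking additional treatment, not seeking additional treatment". The other is "to complete as many of the patient-reported outcomes questionnaires as possible". The wound-status list is introduced by i.e. rather than e.g., so it reads as complete. What is learned is "counted toward the actual follow-up rate, but used only for the analysis of tertiary endpoints".

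The tertiary outcome measures in Section 3 include the incidence of adverse events.

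Two other sections bear on events that arise away from a visit. Section 5.5 states: "The investigator should document any reported adverse events that occur outside of interval visits". Section 7.1 makes the investigator and staff responsible for documenting all AEs as defined in 7.3, and has a sponsor-designated monitor "review patient medical records at the study locations for indications of adverse events throughout the study".

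Section 8.1 tabulates AE rates by type, severity and relatedness. It gives no denominator, no observation period and no rule for withdrawn patients. The schedule in Appendix A places the AE form at treatment-period visits and has no entry for the withdrawal contact.

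**The concern.** The point is about how AEs are found, not about the denominator for wound closure. Followed as written, active inquiry about AEs ends at the last visit the patient attends. The contact made afterwards is credited to follow-up and is eligible for the AE analysis, yet it asks nothing that would produce an AE record. The plan can therefore report a follow-up rate that is more complete than its safety ascertainment.

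Section 2.1 names initial safety as a purpose, alongside informing a randomized trial. There is one arm and no concurrent control, so no comparison within the study would expose a shortfall in the AE count. It is plausible that some patients leave a foot-ulcer study because the foot is getting worse. Because 5.6 does not collect the reason for leaving, the study could not check whether that happened.

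**Working it through.** The documents give no withdrawal rate, no expected AE rate and no precision target, so there is no planned figure to reproduce. The check is first a comparison of the sections, then an illustration on stated assumptions.

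**Step 1. What the contact yields against what an AE record needs.** Section 5.5 requires type, severity and relatedness. The four wound-status answers supply none of these. A patient admitted elsewhere with a foot infection could truthfully answer that the wound is not healed and that treatment is being sought. Nothing in 5.6 would then require a further question.

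**Step 2. Routes that remain after the last visit.**
- Section 5.5 covers events that are reported. It is passive, so it works if the patient volunteers the event.
- The monitor's review in 7.1 covers records at the study locations. Care given elsewhere need not appear there.
- The general duty in 7.1 to document all AEs applies to events the site knows of. It does not add a question to the contact.

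**Step 3. Is the information admitted to the AE analysis?** Yes. Section 5.6 restricts its use to tertiary endpoints, and AE incidence is one. The gap is in asking, not in permission to use the answer.

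**Step 4. Size.** Inputs:
- n = 30 (Section 3; Section 1 calls it a minimum).
- Withdrawals w = 3 to 6, that is 10% to 20% of 30 (assumed).
- Fraction f of withdrawn patients with a missed event after the last visit and no earlier recorded AE: 0 to 1/2 (assumed).
- Crude incidence taken as patients with any AE divided by all 30 (assumed, since 8.1 does not define it).

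Formulas: patients missed m = w × f; understatement = m / n.
- One patient: 1/30 = 3.3 points.
- Lowest: m = 3 × 0 = 0, so 0/30 = 0 points.
- Highest: m = 6 × 1/2 = 3, so 3/30 = 10.0 points.

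To see this against sampling error, suppose 6 of 30 patients truly have an AE (assumed). Intervals are exact (Clopper-Pearson) 95%.

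| Patients missed | Reported | 95% CI |
|---|---|---|
| 0 | 6/30 = 20.0% | 7.7% to 38.6% |
| 2 | 4/30 = 13.3% | 3.8% to 30.7% |
| 3 | 3/30 = 10.0% | 2.1% to 26.5% |

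With three missed, the upper limit falls by 38.6 − 26.5 = 12.1 points, and the interval carries no sign that anything is missing. The outer bound, if all 6 of 6 withdrawn patients had a missed event, is 6/30 = 20.0 points. Nothing in the documents suggests that case.

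**The case against.** The strongest reply is that the plan leaves routes for these events to be recorded. A reader might infer from 5.6 that withdrawn patients contribute no events after their last visit. The documents do not support that. Volunteered events fall under 5.5, 7.1 requires all AEs to be documented, and the monitor reviews site records throughout the study. Asking whether the patient is seeking further treatment may also prompt disclosure. This stands, and it is why the range starts at zero.

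A reader might also infer that the missed events are the most severe ones. No section gives reasons for withdrawal or links withdrawal to severity, so that is conjecture. Harm that leads to withdrawal would often be seen first at a weekly visit, where infection is looked for. A later event in a patient with a recorded AE leaves patient-level incidence unchanged. This stands too, and limits the 3.3-point effect to patients with no earlier AE.

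On follow-up, 5.6 counts information obtained, so on its natural reading patients who are never reached are not counted. Nor does 8.1 make the follow-up rate the AE denominator. The overstatement is therefore confined to patients who were reached but not asked about AEs.

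Finally, the AE window is not defined. Section 7.2 mentions a reporting period without giving its end, 7.3 refers to the course of the study, and 7.4 to the end of study for each patient. If that end is withdrawal, later events are out of scope. The plan does not say so, and 5.6 goes on collecting tertiary-endpoint information after withdrawal. This is a reason to define the period, not a reason to leave the contact as it is.

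The study is also a descriptive series with no safety threshold tied to the AE rate. That limits the weight of the point but does not remove it, since initial safety is a stated purpose.

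**Conclusion.** The point holds in this form: withdrawn patients are not actively asked about AEs or why they left, so events after the last visit may be under-ascertained, and the follow-up rate may overstate how completely safety was followed. The size is 0 to 3 patients, or 0 to 10 percentage points of crude incidence. This rests on assumed withdrawal of 3 to 6 of 30, an assumed zero to one half of those having a missed event, no earlier AE in those patients, and a denominator of 30. Only the sample size comes from the documents; with more than 30 patients, each missed patient weighs less. Whether harm drives withdrawal is unknown, and the plan as written would not find out. This is a correctable gap in data collection that should be closed. It does not invalidate the study.

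**What to change.** In Section 5.6, add two items to the contact already planned:
- the reason for withdrawal;
- a direct question on adverse events as defined in 7.3 since the last visit, naming infection, hospitalization and amputation, with any answer entered on the AE form with onset date, severity and relatedness.

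In Section 8.1, state that AE observation for each patient ends at the last visit or contact at which AEs were asked about, and report how many withdrawn patients were not reached.

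The cost is a few more minutes per contact and a line or two of reporting. The AE rate may come out less favourable. Treatment and the visit schedule are unchanged.
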